#### Trial 03-133

As of 30 June 2019, the most common adverse events (AEs) ( $\geq 10\%$ ) were lymphopenia, platelet count decreased, white blood cell count decreased, neutrophil count decreased, vomiting, hemoglobin decreased, cough, headache, contusion, diarrhea, rhinorrhea, decreased appetite, pyrexia, abdominal pain, and nausea. The most common serious adverse events ( $\geq 5\%$ ) were platelet count decreased, neutrophil count decreased, and white blood cell count decreased. Less frequent, but clinically significant serious adverse events ( $< 5\%$ ) include myelodysplastic syndrome, acute myeloid leukemia, seizure, and depressed level of consciousness. 10% of patients discontinued from treatment with I-omburtamab due to adverse events, including decreased platelet count, chemical meningitis, and immune thrombocytopenic purpura. Serious infusion reactions included chemical meningitis, vomiting, pyrexia, headache, and nausea.

## Trial 101

As of 01 Jun 2020, the most common AEs ( $\geq 10\%$ ) were platelet count decreased, white blood cell count decreased, lymphocyte count decreased, neutrophil count decreased, nausea, headache and anemia, vomiting, pain, and pyrexia. The most common serious adverse reaction ( $\geq 10\%$ ) was platelet count decreased. Less frequent, but clinically significant serious AEs related to  $^{131}\text{I}$ -omburtamab administration were chemical meningitis and intracranial hemorrhage. The most common AE leading to discontinuation of  $^{131}\text{I}$ -omburtamab was platelet count decreased. Serious infusion reactions occurred in one patient (chemical meningitis).

## Selected AEs in Trials 03-133 and 101

Myelosuppression is caused by radiation-related adverse effects on the bone marrow and may result in severe and prolonged cytopenia. In Trial 03-133 and Trial 101, a total of 81.7% and 87.5%, respectively, had at least one event related to cytopenia. The most commonly reported hematopoietic cytopenia events were lymphopenia, platelet count decreased, and white blood cell count decreased.

Chemical meningitis is an inflammation of the meninges. Symptoms include fever, headache, nausea, and vomiting. Three patients experienced SAEs of chemical meningitis (2/109 and 1/24 in Trial 03-133 and Trial 101, respectively).

## Serious infusion reactions in Trials 03-133 and 101

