### 2.2. Endpoints

#### 2.2.1. Primary Endpoints

The primary endpoint of Part 1 is number of DLTs.

The primary endpoint of Part 2 is number and severity of TEAEs.

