### ***3.1.1.2. Definition of Dose-limiting Toxicity***

DLTs are defined as AEs (graded according to CTCAE version 5) occurring within 5 weeks after first IMP administration in Cycle 1 of Part 1 and that are considered possibly or probably related to IMP and meet any of the following criteria:

- Grade 4 myelosuppression (i.e., anemia, thrombocytopenia, or neutropenia) lasting more than 1 week, or more than 3 weeks following intervention (e.g., blood transfusion or granulocyte-macrophage colony-stimulating factor [GM-CSF])
- Any other Grade 4 hematological AE
- Grade  $\geq 3$  thrombocytopenia associated with bleeding
- Grade  $\geq 3$  febrile neutropenia (i.e., fever concurrent with neutropenia) lasting more than 5 days despite use of growth factors and antibiotics
- Grade 4 infusion-related reactions/anaphylaxis
- Grade 3 infusion-related reactions (excluding fever and Grade 3 abnormal laboratory values) that do not resolve to Grade  $\leq 1$  within 5 days of onset.
- Any non-hematological Grade  $\geq 3$  AE that is not listed in the list of exemptions below

DLTs must be entered onto the clinical AE report form and be reported from site to sponsor within 24 hours of the investigator's first knowledge of the event (see [Section 7.4.5.2](#)). If any of the side effects mentioned in the DLT definitions occur during Cycle 2 in Part 1, these will be discussed at the first upcoming preplanned DMC meeting, and the Sponsor Safety Committee will evaluate the DMC recommendations for further dosing.

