### **8.5.2. Adverse Events**

The Safety Analysis Set will be used for all safety analyses except for evaluations of DLTs. Adverse events will be coded using the Medical Dictionary for Regulatory Activities (MedDRA) Version 22.1 or later. Adverse events will be regarded as TEAEs if they occur after first administration of Lu-DTPA-omburtamab. Related AEs are defined as ADRs.

Listings will be made of all AEs. Non-TEAEs will be listed separately. All TEAEs, ADRs, AESIs, SAEs, and serious ADRs will be summarized by MedDRA SOC and preferred terms for each treatment group. The summaries will include number of AEs, number of patients, and percentage of patients reporting these AEs and will be tabulated by SOC and preferred term. TEAEs will also be summarized by severity and by relationship to IMP.

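### The Part 2 safety tables have no pooled cytopenia category, so they would not give the number of patients with any cytopenia or their worst grade

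*Combined protocol and SAP*

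**What the plan says.** Section 2.2.1 sets the endpoint: "The primary endpoint of Part 2 is number and severity of TEAEs". Section 8.5.2 sets the coding ("Adverse events will be coded using the Medical Dictionary for Regulatory Activities (MedDRA) Version 22.1 or later") and the form of the summaries, which show event counts, "number of patients, and percentage of patients reporting these AEs and will be tabulated by SOC and preferred term". It continues: "TEAEs will also be summarized by severity and by relationship to IMP". All adverse events are also listed. The synopsis gives the same plan in shorter form. Neither place names a grouped term, a standard query, a list of synonyms or a rule for counting a patient once at worst grade across related terms.

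Elsewhere the protocol does use the grouped idea. Section 1.2.1 reports for the two iodine-131 trials that "a total of 81.7% and 87.5%, respectively, had at least one event related to cytopenia". The DLT definition in Section 3.1.1.2 includes "Grade 4 myelosuppression (i.e., anemia, thrombocytopenia, or neutropenia", and the dose-delay rule in Section 5.3.1 refers to myelosuppression as one entity. Section 1.2.3 describes myelosuppression as the main toxicity seen with the iodine-131 product, though not a dose-limiting one. Section 1.1 gives the hope of less of it as a reason for using lutetium-177.

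**The concern.** The trial's main expected toxicity belongs to a family of related terms, and the planned tables report the members of that family separately. The first question for a reader of the Part 2 safety results is how many of the 24 patients had a cytopenia, and how bad it was. That is a count over the union of several rows, and it cannot be recovered from a table that shows only the rows.

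A second, conditional problem is that one cytopenia can be recorded under two names. Section 7.4.5 asks the investigator for the diagnosis if there is one and otherwise for the individual signs and symptoms. Section 7.4.1 makes a clinically significant laboratory abnormality an adverse event in its own right. Both naming styles are therefore legitimate, across about 9 + 2 = 11 sites. If both are used, each row falls below the patient-level rate for that cytopenia.

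**Working it through.** **1. The plan's own figure.** Section 8.1 states at least 90% probability of detecting, in 24 patients, an event that occurs in 10%. The probability of at least one case is 1 − 0.90^24 = 1 − 0.080 = 0.920. The statement is correct. It concerns seeing the event at all, under any name, so the layout of the tables does not change it.

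**2. The background rates are pooled.** 89/109 = 81.7% and 21/24 = 87.5%, using the 109 and 24 neuroblastoma patients in Section 1.2.1. The numerators are inferred, but both rates fit whole patients counted once for any cytopenia-related event.

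**3. Any cytopenia, with uniform coding.** Let n1, …, nk be the patient counts in the k cytopenia rows, and U the number of patients in at least one of them. The rows alone give only

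max(n1, …, nk) ≤ U ≤ min(24, n1 + … + nk).

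As an illustration (assumed counts), take two rows for different cell lines with 12 of 24 patients each. Then U lies between 12 and min(24, 12 + 12) = 24, that is, between 50% and 100%. A third row cannot lower the upper bound, and raises the lower bound only if it exceeds 12. The worst grade per patient across rows has the same problem. This step needs no assumption about how sites choose terms.

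**4. One cytopenia under two synonyms.** Let T patients be affected: a under one term, b under the other, c under both. Then T = a + b − c, so the larger row is at least (T + c)/2, hence at least T/2, and at most T. It therefore understates T by anything from nothing to one half. With T = 12 of 24 (assumed, 50.0%) and c = 0:

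- all under one term: 12/24 = 50.0%, no understatement
- 75:25 split: 9/24 = 37.5% and 3/24 = 12.5%
- 50:50 split: 6/24 = 25.0% in each row

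The documents give no split.

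**5. Evidence that synonyms occur.** The lists in Section 1.2.1 are "lymphopenia, platelet count decreased, white blood cell count decreased, neutrophil count decreased, vomiting, hemoglobin decreased" (start of the Trial 03-133 list) and "platelet count decreased, white blood cell count decreased, lymphocyte count decreased, neutrophil count decreased, nausea, headache and anemia" (Trial 101). Set beside the myelosuppression item of the DLT definition:

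| Cell line | Trial 03-133 | Trial 101 | DLT item |
|---|---|---|---|
| Lymphocytes | lymphopenia | lymphocyte count decreased | not named |
| Hemoglobin | hemoglobin decreased | anemia | anemia |
| Platelets | platelet count decreased | platelet count decreased | thrombocytopenia |
| Neutrophils | neutrophil count decreased | neutrophil count decreased | neutropenia |
| White cells | white blood cell count decreased | white blood cell count decreased | not named |

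In reported adverse events the name differs for two of the five cell lines, and only between trials. For platelets and neutrophils the second name appears only in definitional text.

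**6. Whether another planned output fills the gap.** The severity and relationship summaries pool no terms. A SOC total counts anyone with any event in that class, and nothing in the plan restricts such a total to cytopenias. Section 8.5.3 examines hematology changes, but shifts are optional and run only from normal to abnormal. Section 4.1 admits patients with hemoglobin from 8 g/dL, neutrophils from 1000/µL and platelets from 75,000/µL. A child who enters with low counts would not appear in such a shift, however far the counts fall.

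**The case against.** The strongest reply is that this is a reporting refinement and no stated figure is wrong. The plan does more than tabulate by SOC and preferred term: it summarises severity and relationship, lists every event, records the worst grade of each event (Section 7.4.5) and examines hematology changes. Coded, listed data can be pooled later. Part 2 is single-arm and descriptive, and nothing in Section 8.5 proposes a comparison with 81.7% or 87.5%. Those rates come from neuroblastoma patients given the iodine-131 product for up to 2 cycles, not medulloblastoma patients given the lutetium product for up to 5.

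Much of this stands. It rules out several stronger readings that a reader might infer:

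- *That every cytopenia will be split.* The documents show two naming styles in adverse-event data for lymphocytes and hemoglobin only, and between trials rather than within one table. With consistent coding, a single-cytopenia row is right.
- *That the halves would fall in different SOCs.* The documents do not give the MedDRA hierarchy, so this cannot be established from them.
- *That splitting undermines the sample-size statement.* That statement is about detecting an event, not filling a row, and it holds at 92.0%. Detection is not the issue for a toxicity the programme saw in most patients.
- *That Part 2 will show cytopenia at the earlier rates.* The population, product and number of cycles differ.

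The reply does not remove the union problem, which holds under perfect coding. Later pooling is possible, but in an open-label trial the groups would then be chosen after the events had been seen.

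**Conclusion.** The point holds as a gap in the planned summaries, worth closing because it is cheap and concerns the primary endpoint. As written, Section 8.5.2 would not give the number of Part 2 patients with any cytopenia, or their worst grade across related terms. That conclusion rests only on the absence of a pooled category and on the fact that one patient can appear in several rows.

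Understatement of a single cytopenia is conditional on sites mixing synonyms. Its size is not fixed by the documents: from none to about half in the larger row, for two synonymous terms. The stated detection probability stands.

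**What to change.** Keep the SOC and preferred-term tables. Add to Section 8.5.2 a grouped-term TEAE table with these categories:

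- thrombocytopenia or platelet count decreased
- neutropenia or neutrophil count decreased
- anemia or hemoglobin decreased
- leukopenia or white blood cell count decreased
- lymphopenia or lymphocyte count decreased
- any cytopenia (any of the above)

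Count each patient once per category at worst CTCAE grade, and present the table by relationship to IMP as well. Fix the preferred-term list for each category in writing before the data cut.

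The cost is a paragraph and one or two extra tables. No new data are needed and clinical management does not change. The sponsor should expect that grouped cytopenia rates may look less favourable than the separate rows.

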### **8.5.3. Other Safety Assessments**

Changes in vital signs, hematology, and clinical chemistry parameters from baseline to the end of the trial will be examined. Treatment-emergent changes from normal values to abnormal values in key laboratory parameters may be identified. Development of ADA will be examined. Effects on cognitive functions will be assessed by summarizing changes from baseline in performance testing results using descriptive statistics.

Baseline is defined as the latest assessment prior to first dose.

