Patients will return for an EOT Visit 5 to 6 weeks after the last dose and for regular Follow-up Visits up to 104 weeks after the last infusion of Lu-DTPA-omburtamab to assess safety, efficacy, secondary malignancies, and long-term survival. In addition, all patients who are dosed with Lu-DTPA-omburtamab will be regularly monitored for secondary malignancies (see [Section 7.4.5.3](#)) for at least 10 years after end of trial, or until death, if sooner. This post-trial monitoring can be conducted by contacting the patient or the general practitioner, the referral site (if applicable), or by checking medical records or other sources.

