#### **4.3.3. *End of Trial***

The end of the trial is defined as the date the last patient completes the last Visit or the date of death of the last patient, whichever comes first.

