### **7.4.5.1. *Events Requiring Immediate Reporting***

The following events (for reporting periods, see [Figure 2](#)) require immediate reporting (within 24 hours) (for details, see [Section 7.4.5.3](#)):

- SAE
- DLT
- AESI
- Pregnancy.

Starting five weeks after the last dose, only SAEs or Grade 3 or higher AEs at least possibly related to Lu-DTPA-omburtamab or to the presence of the indwelling catheter system, or new onset of cancers regardless of causality, should be reported until end of trial. Subsequently, in the post-trial monitoring period, SAEs considered related to IMP or new onset of cancers regardless of causality, should be reported until death or at least 10 years after end of the trial, whichever comes first, using the clinical AE report form, see Section [7.4.5.3](#).

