### 8.3. General Considerations

Summary statistics, listings, and statistical analyses will be performed for patients included in the relevant analysis sets.

For continuous data, summary statistics will include the arithmetic mean, arithmetic standard deviation, median, minimum, maximum, and number. For log-normal data (e.g., the PK parameters, the activity-time curve and elimination half-life of absorbed doses to CSF and

blood), the geometric mean and geometric coefficient of variation will be presented instead of mean and SD. For categorical data, frequency counts and percentages will be presented. Data listings will be provided for all patients up to the point of withdrawal, with any patients excluded from the relevant analysis set highlighted. For the calculation of summary statistics, listings, and statistical analysis, unrounded data will be used.

For the time to event efficacy endpoints, patients who do not have an event will be censored at the date of their last evaluation. If partial dates are present, a conservative approach will be used. If partial dates are present for efficacy time to event endpoints, missing months and/or days will be imputed as January and the first day of the month, respectively. AEs with a missing start date or time that leads to ambiguity in whether the AE is treatment-emergent will be considered treatment-emergent. It is unlikely that other missing of safety data will occur in the targeted patient population, but in case it happens the data will not be imputed.

When the last patient in Part 1 has completed the EOT visit, all available data for that part will be reported.

For Part 2, full efficacy and safety analyses will be performed when the last patient completes week 52 assessments, dies, or is lost to follow up. An updated long term survival analysis will be performed when the last patient has reached the 104 week visit, dies, or is lost to follow-up.

Data analysis will be performed using SAS® Version 9.3 or higher.

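### Part 2 TEAEs are defined and collected beyond week 52, but the only planned Part 2 safety analysis is at the last patient's week 52; the week-104 update names survival only

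*Combined protocol and SAP*

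**What the plan says.** - **Endpoint.** Section 2.2.1: "The primary endpoint of Part 2 is number and severity of TEAEs". Section 8.5.2: "Adverse events will be regarded as TEAEs if they occur after first administration of" the study drug. No closing date is given.
- **Collection.** All AEs are collected until 5 weeks after the last dose (Section 7.4.5). After that, Section 7.4.5.1 narrows collection to SAEs and Grade 3 or higher AEs at least possibly related to the product or the catheter, "or new onset of cancers regardless of causality, should be reported until end of trial". Section 4.3.3: "The end of the trial is defined as the date the last patient completes the last Visit", or the last patient's death if earlier.
- **Schedule.** Table 8 puts the last Part 2 visit at week 104 after first dose. It marks AEs, vital signs, performance test and neurological examination at weeks 78 and 104.
- **Purpose.** Section 3.1.3 says that Part 2 follow-up visits are held "to assess safety, efficacy, secondary malignancies, and long-term survival".
- **Other safety data.** Section 8.5.3: "Changes in vital signs, hematology, and clinical chemistry parameters from baseline to the end of the trial will be examined".
- **Analysis timing.** Section 8.3, for Part 2: "full efficacy and safety analyses will be performed when the last patient completes week 52 assessments", dies or is lost. Then: "An updated long term survival analysis will be performed when the last patient has reached the 104 week visit", with the same alternatives. The second sentence does not mention safety.

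**The concern.** The window for the primary endpoint and the window for its analysis do not match. An event in month 18 that meets the TEAE definition is collected and is part of the endpoint. If its patient had not reached month 18 when the last patient reached week 52, no planned summary counts it.

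The events at risk are few in kind but serious: related SAEs, related Grade 3 or higher AEs, catheter-related events and new cancers. The protocol gives reasons to look for them. Section 1.2.1 lists myelodysplastic syndrome and acute myeloid leukemia among the clinically significant SAEs of the iodine-131 product, whose recommended dose was for up to 2 cycles. Part 2 allows up to 5 cycles, and Section 3.2 expects most if not all patients to have had high-dose craniospinal irradiation. How much late follow-up the safety report contains would depend on how fast Part 2 accrues, which is not a safety consideration.

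**Working it through.** **1. The plan's own figure.** Section 8.1 gives at least a 90% chance of seeing an AE of true rate 10% in 24 patients: 1 − 0.9^24 = 1 − 0.080 = 0.920. It reproduces, and nothing below changes it. The plan gives no figure for follow-up beyond the safety cut.

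**2. Is there another planned safety summary after the cut?** Section 4.4 schedules one Part 2 DMC meeting, after the eighth patient's Cycle 1 dosing. Section 8.9 offers only ad hoc interim analyses for regulators. Section 8.5.2 promises AE listings with no date. None is an updated summary of the primary endpoint.

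**3. When does all-grade collection close?** Table 8, footnote 1, puts Cycle 5 Day 1 at Day 141, which is 140 days after first dose. Adding 5 weeks: (140 + 35)/7 = week 25. Section 5.3.1 allows delays of up to 8 weeks before a next cycle. If all four intervals were delayed by the maximum, the window would close at 25 + 4 × 8 = week 57. Most TEAEs therefore fall before the cut.

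**4. How much follow-up lies after the cut?** Assume that 24 patients enrol evenly over A weeks, all are followed to week 104 after first dose, and the cut is at the last enrollee's week 52. A patient enrolled t weeks before the last has 52 + t weeks at the cut, so max(0, 52 − t) weeks come later. With t = kA/23 for k = 0 to 23, and planned follow-up of 24 × 104 = 2,496 patient-weeks:

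- A = 26: 24 × 52 − 12 × 26 = 936
- A = 52: 24 × 52 − 12 × 52 = 624
- A = 104: only k = 0 to 11 count, so 12 × 52 − (104/23) × 66 = 326

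| Accrual (weeks) | Patient-weeks after cut | Share of 2,496 | Patients short of week 78 | Patients short of week 104 |
|---|---|---|---|---|
| 26 | 936 | 37.5% | 23 | 24 |
| 52 | 624 | 25% | 12 | 23 |
| 104 | 326 | 13% | 6 | 12 |

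The documents do not state Part 2 accrual time. The Synopsis estimate for the whole trial, Q4-2021 to Q3-2023, spans at most about 104 weeks and Part 1 comes first, so 104 is the favourable end of the range. If half the patients, spread evenly over enrolment, had no follow-up beyond week 52, the patient-weeks after the cut would halve to 468, 312 and 163.

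**5. Which of the Section 8.5.3 parameters are affected?** Only vital signs are still measured at weeks 78 and 104. Table 8 has no chemistry or hematology there, and footnote 14 stops both at the first follow-up visit (week 26). The cut loses no laboratory data. The Part 2 laboratory problem is a separate one: the text runs to end of trial and the sampling does not.

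**The case against.** The strongest reply is that the week-52 analysis already captures what matters. All-grade collection is normally complete by then, early enrollees bring later data, SAEs continue to reach the sponsor, and the undated listings in Section 8.5.2 could show the late events one by one. Attrition may also be substantial, since Section 3.2 describes limited survival. All of this stands, and it limits the number of events missed. It does not supply an updated count or severity table, which is what the primary endpoint asks for.

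A reader might also infer more than the documents support:

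- *That the primary endpoint is largely unreported.* Step 3 shows otherwise; only the restricted late subset is exposed.
- *That Section 8.5.3 cannot be met for laboratory values at all.* In Part 1, the last column of Table 7 combines end of treatment with end of trial and includes chemistry and hematology. The mismatch is confined to Part 2.
- *That performance and neurological tests are also promised to end of trial.* That phrase in Section 8.5.3 governs vital signs, hematology and chemistry. Performance testing is change from baseline with no stated end, and the neurological examination is not named.
- *That patients go unmonitored.* Visits and reporting continue; this is a gap in analysis and reporting.
- *That a week-104 analysis would settle the cancer risk.* New cancers are followed for at least 10 years after the trial, so it captures only part of it.

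**Conclusion.** The mismatch is real and should be corrected. If Section 8.3 is followed as written, late events that meet the primary-endpoint definition, and week 78 and 104 vital signs, are left out of every planned summary for patients who have not reached those times at the cut.

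The exposed follow-up is about 13% to 37.5% of planned patient-weeks, and less with attrition. This rests on even accrual over an assumed 26 to 104 weeks, complete follow-up, and visits counted from first dose as in Table 8 (Sections 3.1.3 and 3.2 count the 104 weeks from the last infusion). These are shares of follow-up time and not of events; no late-event rate is given, so none is assumed.

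**What to change.** In Section 8.3, make the week-104 update an updated safety and survival analysis:

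- Re-run the Section 8.5.2 summaries on all data to week 104: TEAEs by severity and by relationship, ADRs, AESIs and SAEs, with new cancers shown.
- Re-run the vital-sign and performance-status summaries on the same data.
- Label the week-52 output as the primary safety output and the week-104 output as the final one.
- Show TEAEs by onset, up to versus after 5 weeks from the last dose, because collection is restricted in the later period and the two counts are not comparable.

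Separately, and for Part 2 only, align the laboratory wording in Section 8.5.3 with Table 8, footnote 14, so that it ends at the first follow-up visit. Leave Part 1 unchanged and do not extend sampling.

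The cost is a short text change and one extra table run, with the onset split added, at a time when an analysis is already planned. No patient, visit or sample is added.
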